6 STUDY ASSESSMENT AND TREATMENT SCHEDULE (PHASE

The table below lists all of the required assessments that should be performed at each study visit for subjects enrolled to the Phase 3 stage of the trial (version 3.0+).

TABLE 5: STUDY ASSESSMENT AND TREATMENT SCHEDULE

							_										
EOS,8				×			X			X	X	×					
LTFU7																	
30-and 90-Day Safety FU ⁶																	
ЕОТ				×			X			X	X	X					
Cycle 18 and Q3 Cycle ⁵	D1			X			X		X	X	X	×					X
Cycles 9, 12, 15 ⁵	D1			×			X		X	X	X	×					X
Cycles 5&6³	D1			X			Х		X	X	X	X					X
	D22									X		×					
Cycle 4 ⁴	D15									X		×					
Cyc	D8									X		X12					
	D1			X			X		X	X	X	X11					X
Cycles 2-3³	D1			X			X		X	X	X	×					
	D15									X	X	X					
Cycle 1 ²	D8									X	X	×					
Cy	D2									X	X	X					
	D1			×			X		X	X	X	×					
Screening ¹	D-30 to D0	X	X	X			X		X	X	X	X			X	X	X
Cycle = 28 days	Procedure/Days	Medical history	Rai Staging	ECOG	Performance	Status	Physical	Examination	Weight	Vital signs ⁹	Hematology ¹⁰	Chemistry, LDH,	Mg, Phos, Uric	acid10	PT/INR13	Hep B/C14	CMV15

Screening labs (hematology and chemistry only) must be conducted within 14 days prior to Cycle 1 Day 1. Patients must continue to meet eligibility criteria in respect to adequate organ system function as per Inclusion Criteria # 2 within the required screening timeframe, and importantly, on Cycle 1 Day 1. Hematology and chemistry results must be reviewed prior to dosing on Cycle 1 Day 1 to ensure subjects meet Inclusion #2 as per

² Study visits have a ±1 day window.

³ Study visits have a ±3 day window.

[·] Cycle 4 Day 8, 15, and 22 visits only for subject randomized to Arm A (U2-V). Study visits have a±3 day window.

⁵ Study visits have a ± 7 day window.

^{&#}x27;Subjects who discontinue from study treatment (for reasons other than progressive disease) will continue to be followed for progression until a non-protocol line of therapy is initiated. LTFU for PD and OS should be s A 30-day (± 7 days) and a 90-day (± 7 days) safety follow up visit is required after the last dose of study drug. See Section 12.2.3 Adverse Event/Serious Adverse Event Recording. entered approximately every 6 months. Enter date of disease progression and/or death occurred in eCRF.

Bind of Study (EOS) visit to be completed for subjects who are coming off study. Tumor Assessment should be performed if not done within previous 3 months. EOT and EOS may be the same visit if subject is discontinuing

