12.2.3 Adverse Event/Serious Adverse Event Recording

¹⁷ For females of childbearing potential, serum pregnancy test completed within 3 days prior to Day 1 of Cycle 1.

¹⁸ For females of childbearing potential. This is only required if patients are receiving drug.

²⁰ IgHV to be done at screening if mutation status is not already known.

¹⁹ Baseline BM as clinically indicated as per standard of care. Post-baseline BM biopsy to confirm potential CR required.

²¹ FISH central lab results required for randomization. Samples for FISH, and NGS to be sent to the Central Lab, see lab manual for sample collection and shipment procedures.

²² MRD in peripheral blood at baseline and Cycle 6, Cycle12, Cycle 15 and Cycle 24 (MRD drawn only if subject is in PR or better). One MRD by bone marrow aspirate sample should be completed for all patients MRD negative by peripheral blood. Thereafter, all subjects without signs of clinical progression, repeat MRD every 6 cycles (peripheral blood). Subjects that end treatment prior to Cycle 15 should continue to have MRD collected until month 15. See laboratory manual for collection, processing, and shipment instructions.

²³ A total of 2 serum samples should be collected from each subject for sparse population PK analyses (Pre-dose on Cycle 4, Day 1, and one randomly assigned post-baseline sample). See Section7.2.1 Sparse Sampling **Pharmacokinetics**

²⁴ Samples to be collected pre-dose of ublituximab

²⁵ Response assessment at baseline (within 30 days prior to Cycle 1 Day 1), and within 14 days prior to Cycles 4 & 12, and at least every 6 cycles thereafter. Radiologic assessment should include CT with contrast or MRI imaging of neck, chest, abdomen, and pelvis. BM biopsy to confirm potential CR required. If PD is suspected, scans and relevant clinical data should be sent to central radiology for expedited PD review. This PD confirmation should be obtained prior to subject being removed for PD (except in rare cases where it is in the patients best interest to be discontinued immediately.

²⁶ Venetoclax Cohort Only: TLS risk assessment according to Section 8.5.3.1 at baseline and on Day 1 of Cycle 4, prior to first dose of venetoclax.

27 AEs are to be reported from Cycle 1 Day 1 and SAEs are to be reported from signing of informed consent. A 30-day (± 7 days) and a 90-day (± 7 days) safety follow up visit is required after the last dose of study drug. See Section

Dated: 05 October 2021 (Ver 4.0) U2-VEN-207

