8 TREATMENT PLAN

8.1 TREATMENT SUMMARY

Treatment will be administered in 28-day cycles. Patients must continue to meet eligibility in respect to adequate organ system function as per Inclusion Criteria #2 on Cycle 1 Day 1. Hematology and chemistry results must be reviewed prior to dosing on Cycle 1 Day 1 to ensure subjects meet Inclusion Criteria #2 as per the protocol.

Please see Section 8.5.3: Guidelines for Administration of Venetoclax for specific information on TLS risk, prophylaxis and assessments.

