8.5.2.2 DOSE HOLD/MODIFICATION: UMBRALISIB

Supportive care should be considered for any subject who experiences $Grade \ge 2$ cytopenias, or $Grade \ge 1$ non-hematologic toxicities. If a subject experiences a treatment-related AE requiring dose modification during the course of therapy, then study drug administration should be held, as necessary, until the AE resolves or stabilizes to an acceptable degree. In addition, the subject should be notified of the change in dose and the appropriate clinic staff should instruct the subject about the revised number of study medication tablets to be used per dose according to the new dose level. Any questions regarding dose modification should be referred to TG Therapeutics.

The adjunctive supportive care recommendations listed in the dosing hold and modification tables are meant to serve as guidelines and are not meant to replace Investigator discretion. Final toxicity

U2-VEN-207

management decisions are the responsibility of the clinical Investigator. However, adherence to study drug dose hold, dose reduction, and dose discontinuation criteria are strongly advised for patient safety reasons. Please contact the Sponsor with any questions related to managing side effects, holding treatment or other dose modifications. If a subject discontinues only one study drug, the subject may continue treatment with the other study drug(s) per the protocol. Please see Table 22 for further guidance.

TABLE 18. STUDY DRUG DOSE REDUCTION RECOMMENDATIONS

Study Drug	Starting Dose	1st Dose Reduction	2 nd Dose Reduction
Umbralisib	800 mg	600 mg	400 mg

A maximum of 2 dose level reductions are allowed for umbralisib.

If a subject requires a dose reduction of umbralisib due to study drug-related AE, the dose may not be re-escalated. If further evaluation of the toxicity reveals the AE was not related to umbralisib, this must be recorded in the medical record and dose re-escalation to the next higher dose level may be considered at the discretion of the Investigator.

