8.5.4 DOSE HOLD/MODIFICATION: UBLITUXIMAB, UMBRALISIB AND VENETOCLAX

Table 22 illustrates the dose hold and modifications for all investigational products in the present study.

Subjects should be assessed clinically for toxicity at each visit using the NCI CTCAE v5.0 (https://ctep.cancer.gov/protocoldevelopment/electronic_applications/docs/ctcae_v5_quick_reference_5x7.pdf) grading scale.

Dose hold and/or modification guidance is for adverse events considered *related* to the study drug(s). If the adverse event is *not considered related* to a study drug (ublituximab, umbralisib and/or venetoclax), then that drug does not need to be modified or held as per Investigator assessment.

If cytopenias are deemed related to the underlying disease rather than study drug, dose modifications are not required, or are per investigator discretion. If a subject discontinues one or more study drugs, the subject may continue treatment with the other study drug(s) per the protocol.

U2-VEN-207

Dose reduction and/or holds are permitted as per Investigator discretion to manage adverse events related to one or more of the study drugs. The guidelines below are recommendations and are not meant to replace Investigator discretion.

TABLE 22. STUDY DRUG MODIFICATIONS

	Ublituximab	Umbralisib	Venetoclax	
NCI CTCAE Grade				
Neutropenia				
Grade 1-2 neutropenia	Maintain full dose. Consider growth- factor support as warranted.	Maintain current dose. Consider growth-factor support as warranted.	Maintain current dose. Consider growth-factor support as warranted.	
Grade 3 neutropenia	Maintain full dose. For recurrent or persistent Grade 3 neutropenia hold ublituximab until Grade ≤2, then resume. Consider growth- factor support as warranted.	Maintain current dose. If recurrence or persistent Grade 3, hold umbralisib until Grade ≤ 2 and resume at same dose. Consider growth-factor support as warranted.	Maintain current dose, if Grade 3 recurs or is persistent then hold venetoclax until ≤ Grade 2, after resume at the same dose. Consider growth-factor support as warranted.	

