Grade 4 neutropenia or occurrence of Neutropenic fever or infection	Hold ublituximab until Grade ≤ 3 and/or neutropenic fever or infection is resolved; consider growth factor support as warranted; thereafter, resume at full dose	Hold umbralisib until Grade ≤3 and/or neutropenic fever or infection is resolved; thereafter, resume umbralisib at current dose. Consider growth- factor support as warranted. If recurrence after rechallenge despite maximum supportive care, hold umbralisib until ≤ Grade 3; thereafter resume umbralisib at next lower dose level.	Hold venetoclax until Grade ≤3 and/or neutropenic fever or infection is resolved; thereafter, resume venetoclax at current dose. Consider growth- factor support as warranted. If recurrence after rechallenge despite maximum supportive care, hold venetoclax until ≤ Grade 3; thereafter resume venetoclax at next lower dose level.	
Thrombocytopenia				

U2-VEN-207

	Ublituximab	Umbralisib	Venetoclax	
	Ublituximab	Umbralisib	Venetoclax	
Grade 3 thrombocytopenia	Maintain full dose.	Maintain current dose.	Maintain current dose.	
Grade 4 thrombocytopenia	Hold ublituximab until Grade ≤ 3; thereafter resume at full dose.	Hold umbralisib until Grade ≤3; thereafter, resume umbralisib at current dose. If recurrence after rechallenge despite maximum supportive care, hold umbralisib until ≤ Grade 3; thereafter resume umbralisib at next lower dose level.	Hold venetoclax until Grade ≤3; thereafter, resume venetoclax at current dose. If recurrence after rechallenge despite maximum supportive care, hold venetoclax until ≤ Grade 3; thereafter resume venetoclax at next lower dose level.	
Infection (including opportunistic infection)				
	Ublituximab	Umbralisib	Venetoclax	
Grade 2 infection	Consider dose hold and/or supportive care as per investigator discretion.	Consider dose hold and/or supportive care as per investigator discretion.	Consider dose hold and/or supportive care as per investigator discretion.	
Grade 3 or 4 infection	Withhold ublituximab until resolved, then resume at full dose.	Withhold umbralisib until resolved, then resume at same or reduced dose.	Withhold venetoclax until resolved, then resume at same or reduced dose.	

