11.11 STATISTICAL ANALYSES

11.11.1 PRIMARY EFFICACY VARIABLES

11.11.1.1 PROGRESSION-FREE SURVIVAL (PHASE 3)

PFS is defined as the number of days between randomization and the date of progression (as confirmed by the IRC) or death due to any cause, whichever occurs first. Subjects who had no event (progression or death) will be censored at the day of their last adequate disease assessment. If no baseline or post-baseline assessment is available, the subject will be censored at the date of randomization. If death or PD occurs after 2 or more consecutive missing disease assessments, censoring will occur at the date of the last adequate disease assessment prior to the missed assessments. The use of a new anticancer therapy prior to the occurrence of PD will result in censoring at the date of last adequate disease assessment prior to initiation of new therapy.

Hypothesis testing for comparison between the treatment arms will be performed using a stratified (by randomization stratification factors) log-rank test via SAS Lifetest procedures. For each treatment arm, the median duration of PFS and the proportion of subjects alive and progression-free at 6, 12, 24, and 36 months will be estimated using the Kaplan-Meier method. For each estimate, a 95% confidence interval will be reported. The hazard ratio with 95% confidence interval will be estimated by stratified (by randomization stratification factors) Cox proportional hazards model.

U2-VEN-207

Sensitivity analyses will be conducted, including using investigator assessment of PFS, using different censoring rules (ignoring new anti-cancer therapy, ignoring 2 or more consecutive missing assessments). In addition, the potential impact of COVID-19 on patients for the efficacy results may be included in the sensitivity analysis (censoring all subjects at the last adequate assessment if subject discontinued study or death due to COVID-19). Other sensitivity analyses may be conducted as needed.

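### Phase 3 scans are timed by cycle number with no calendar anchor and no rule for postponed cycles, so unequal cycle delay would bias PFS toward the more delayed arm; the likely size is small

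*Combined protocol and SAP*

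**What the plan says.** Section 6, Table 5, footnote 25 sets the Phase 3 response assessments at baseline, then "within 14 days prior to Cycles 4 & 12, and at least every 6 cycles thereafter". No visible passage gives on-treatment scans a date in weeks from randomization. Section 8.1 states "Treatment will be administered in 28-day cycles", and for Cycle 9 onward Table 5 adds "Study visits have a ± 7 day window".

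The primary endpoint runs on a different clock. Section 11.11.1.1 reads "PFS is defined as the number of days between randomization and the date of progression (as confirmed by the IRC) or death".

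Holds have no stated maximum length. Section 8.5.2.2 says "study drug administration should be held, as necessary, until the AE resolves or stabilizes to an acceptable degree". Table 22 in Section 8.5.4 holds all three drugs for several events; for Grade 4 neutropenia, neutropenic fever or infection the venetoclax entry is "Hold venetoclax until Grade ≤3 and/or neutropenic fever or infection is resolved". The drugs are handled one by one: "If a subject discontinues one or more study drugs, the subject may continue treatment with the other study drug(s) per the protocol". Nothing says whether a hold, of one drug or of all, moves Day 1 of the next cycle.

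Section 11.11.1.1 censors a progression or death that follows two or more consecutive missing assessments. Its listed sensitivity analyses cover investigator assessment, alternative censoring rules and COVID-19, but not the timing of assessments.

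**The concern.** Progression that shows only on imaging is dated at the scan that finds it. If a held dose pushes back the next cycle, footnote 25 pushes back the scan as well, and the patient gains recorded progression-free time without any treatment effect. Scheduled scans are 24 to 32 weeks apart, so events cluster at scan dates, and a log-rank test responds to a small systematic shift in those clusters between arms.

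The arms also differ in ways that could make delay unequal. Only Arm A has the venetoclax ramp-up. Table 10 fits its steps into the four weeks of Cycle 4, and Table 21 requires a reduced ramp-up dose to be kept for a week before it is increased. An interrupted ramp-up would then overrun a 28-day Cycle 4, and the protocol does not say whether Cycle 5 starts late. Arm B, on the other hand, is treated without a fixed end and can accumulate delay for longer.

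The missing-assessment rule is affected too. Without calendar due dates, a late scan and a missed scan are hard to tell apart, and that distinction can decide whether an event counts.

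**Working it through.** **1. Nominal calendar.** The start of Cycle k falls at 28 x (k - 1) days after Cycle 1 Day 1.
- Cycle 4: 28 x 3 = 84 days = week 12.
- Cycle 12: 28 x 11 = 308 days = week 44.
- Six cycles: 28 x 6 = 168 days = 24 weeks, so Cycle 18 starts at week 44 + 24 = 68.
- Arm A treatment ends after Cycle 15: 28 x 15 = 420 days = week 60.

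Only the Cycle 4 and Cycle 12 scans named in footnote 25 therefore fall within Arm A treatment.

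**2. The mechanism in one patient.** Suppose cycles slip by 14 days in total before Cycle 12. A silent progression at day 200 is then dated up to day 322 instead of up to day 308. If the cycles do not slip, nothing changes.

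**3. The plan's own figures.** Sections 11.11.3 and 11.11.4 test PFS at a final two-sided level of 0.0462, or 0.0231 one-sided (z = 1.994). The critical HR is exp(-2z / sqrt(d)):
- d = 172: exp(-3.987 / 13.115) = 0.738; the plan states 0.74.
- d = 122: exp(-3.987 / 11.045) = 0.697; the plan states 0.70.

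**4. Effect on PFS when Arm A is delayed more.** The documents give no hold rates and no visible median PFS, so these inputs are assumptions: exponential PFS with median 24 or 36 months in both arms (no true effect), scans at weeks 11, 43 and every 24 weeks after, 15% of events deaths with exact dates, and mean cumulative delay of 2-6 weeks in Arm A against 1-2 weeks in Arm B. The simulated HR is about 0.97-0.99, with one-sided error of about 2.2%-3.9%. The lower end is below the nominal 2.3% only through simulation noise.

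The approximation 1 - Phi(1.994 + ln(HR) x sqrt(d) / 2) agrees:
- HR 0.97, d = 172: 1 - Phi(1.994 - 0.200) = 3.6%; d = 122: 3.4%.
- HR 0.99, d = 172: 1 - Phi(1.994 - 0.066) = 2.7%; d = 122: 2.6%.

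**5. Dependence on direction and on the delays.** A second simulation of the treatment naive cohort (400 patients, 172 events) used a hold probability per cycle, with every hold postponing the cycle and every progression waiting for a scheduled scan. Expected delay by Cycle 12 is 11 x probability x mean hold length. Arm A's delays stop at Cycle 15; Arm B's continue. The medians are 20, 30 and 40 months.

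| Holds (mean 14 days) | Mean delay by Cycle 12 | HR | False U2-V win |
|---|---|---|---|
| A 25%, B none | 38.5 days vs 0 | 0.928 / 0.963 / 0.979 | 6.5% / 4.2% / 3.3% |
| 15% in both | 23.1 days in each | 1.007 / 1.013 / 1.017 | 1.9% / 2.0% / 1.6% |
| A 5%, B 15% | 7.7 vs 23.1 days | 1.049 / 1.032 / 1.025 | 0.9% / 1.3% / 1.6% |
| Same calendar in both | none | 0.999 at each median | 2.6% / 2.8% / 2.5% |

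The first row is an extreme case, with 5.5 weeks of delay in one arm and none in the other. The second and third rows reverse the direction.

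**6. Imaging on suspicion.** If half of progressions are found without waiting for a scheduled scan, the hold scenarios unfavourable to Arm B shrink to HR about 0.98-0.995. With the delays of step 4 confined to on-treatment scans, the result is HR 0.993-1.002 and error 2.3%-2.6%.

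**The case against.** The strongest reply is that cycles may never move. Table 5 is headed with a 28-day cycle and has narrow visit windows, holds are written drug by drug, the other drugs may continue, and footnote 22 uses Cycle 15 and month 15 interchangeably for MRD. Fixed 28-day cycles with doses skipped is a natural reading, and the bias is then zero. This stands as a possible reading, but the text does not state it, and sites in an open-label trial could differ.

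A reader might infer that the bias favours U2-V because venetoclax adds neutropenia. The documents do not support so firm a statement. The 41% Grade 3/4 rate in Section 1.5 is for venetoclax alone in relapsed or refractory patients; Section 1.6 gives 21% Grade 3 or higher for the triplet among 43 patients. Table 22 keeps the current dose for Grade 3 neutropenia unless it recurs or persists. Umbralisib holds for diarrhea, colitis and liver toxicity apply to both arms. No hold rates by arm are given, and step 5 shows that equal delay rates favour U2.

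A reader might also infer a one-sided error of about 5% or more. That needs a delay almost entirely in Arm A and every progression waiting for a scheduled scan. Section 10.1 requires imaging whenever progression is suspected clinically, and footnote 25 provides expedited central review. These limit the bias, though not for progression visible only on CT.

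Finally, Section 10.2 cites an imaging manual and Section 11 refers further detail to a Statistical Analysis Plan. Neither content is in the reviewed text, and either could already settle delayed visits.

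**Conclusion.** The point holds as a weakness in the scan schedule. Scans follow cycle number, PFS follows days from randomization, and nothing visible links the two when dosing is delayed. If cycles are postponed unequally, PFS is biased toward the more delayed arm. U2-V is a plausible candidate, through the third drug and the ramp-up, but this is not established.

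Under the assumed delays of 2-6 against 1-2 weeks the effect is small: HR about 0.97-0.99 and one-sided error about 2.2%-3.9% against 2.3%. It is close to nil if many progressions are found on suspicion, and absent if cycles never move. These sizes rest on assumed delays and assumed median PFS, not on documented rates. The change is still worth making: it is inexpensive, it removes the timing difference whichever way it runs, and it makes the censoring rule reproducible.

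Arm A's move to follow-up about every six months after Cycle 15 is a separate asymmetry that needs no holds and is not counted in the step 4 figures.

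**What to change.** - Keep the pre-Cycle 4 scan tied to Cycle 4. In Arm A it coincides with the tumor-burden assessment required before venetoclax (Section 8.5.3.1; Table 5, footnote 26). A fixed week-12 scan could miss that point if Cycle 4 slipped, and an extra scan might then be needed.
- Amend footnote 25 so that all later scans in both arms fall at fixed weeks from randomization, for example week 44 and then every 24 weeks, with the same 14-day window, regardless of holds, cycle delays or stopping of one drug, until IRC-confirmed progression. Align the imaging manual.
- In Section 11.11.1.1, define a missing assessment against those calendar dates.
- Add a PFS sensitivity analysis that uses scheduled scan dates or interval censoring.

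The cost is protocol, imaging-manual and analysis wording, with about the same number of scans and no change to dosing. The small downside is that some scans will not coincide with a cycle visit.

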7 LABORATORY ASSESSMENTS

Laboratory assessments will be collected as specified in the study assessments tables. Please see Section 8.5.3.1 for details regarding recommended blood chemistry monitoring based on tumor burden.

7.1 LOCAL LABORATORY ASSESSMENTS

1. Hematologic profile and serum chemistry to include:

TABLE 6. HEMATOLOGIC INDICES AND SERUM CHEMISTRY TO BE PERFORMED LOCALLY

Hema	tologic Profile	
Hematocrit	Neutrophils	Platelet count
Hemoglobin	Lymphocytes	
Erythrocyte count	Monocytes	
Leukocyte count	Eosinophils	
Absolute neutrophil count	Basophils	
Comp	m Chemistry	
Seru		
A 11	_	CCOT [ACT]
Albumin	Creatinine	SGOT [AST]
Albumin Alkaline phosphatase	_	SGOT [AST] SGPT [ALT]
	Creatinine	
Alkaline phosphatase	Creatinine Glucose	SGPT [ALT] Sodium
Alkaline phosphatase Bicarbonate/CO ₂	Creatinine Glucose LDH	SGPT [ALT]

- 2. Quantitative Immunoglobulins (IgG, IgA, IgM)
- 3. Serum β-HCG test for women of child-bearing potential
- 4. Urine pregnancy test for women of child-bearing potential (Phase 3 patients only)
- 5. Coagulation lab tests to include PT and INR
- 6. β2-microglobulin
- 7. Serum virology to include HBsAg, HBcAb, HCV AB, CMV IgG and CMV IgM (site may perform CMV by PCR if that is their SOC). If HBcAb, HCV AB or CMV IgM or IgG is positive, subjects must be evaluated for the presence of active HBV, HCV, or CMV by PCR
- 8. Coombs test (Coombs test not required in subjects enrolled to V3.0 or later)
- 9. BM aspirate/biopsy. (BM for morphology by local laboratory to confirm CR, BM aspirate for MRD assessment to be analyzed at the central laboratory)
- 10. TLS Risk-Assessment as per venetoclax package insert. C4 pre dose labs include CMP, Mg, Phosphorus, uric acid and LDH. Venetoclax post dose ramp up labs include potassium, uric acid, phosphorus, calcium and creatinine.
- 11. IGHV mutation status
- 12. CMV by PCR

[figure not shown]
